## **6 DISSEMINATION POLICY**

### **6.1 Dissemination policy**

The data arising from the study will be owned by the study authors. On completion of the study, the data will be analysed and tabulated, and a Final Study Report prepared, which will be accessible on the Centres for Antimicrobial Optimisation Network (CAMO-NET) website. Participating investigators

can publish any of the study data with permission of the CI. Public participants of the Liverpool AMR Citizens' Jury will be informed of the outcome of the study by provision of the publication. All statistical and BCI code used to generate the results will be made available open source, shared via a GitHub public repository following journal publication.

## **6.2 Authorship eligibility guidelines and any intended use of professional writers**

The main study results will be published as soon as a manuscript is completed, in the name of the study in a peer-reviewed journal, on behalf of all collaborators. The manuscript will be prepared by a writing group composed of the investigators. All investigators will be granted authorship on the final study report in line with International Committee for Medical Journal Editors criteria for individually named authors and group authorship.

## **7 ARCHIVING**

Data and all appropriate documentation will be stored for a minimum of 10 years after the completion of the study within the password-encrypted CIPHA secure data environment, including the follow-up period.

## 9 APPENDICES

**9.2 Appendix 2 – Health Professional Questionnaire**

## ADAPT-AST Protocol

1. A patient presents to General Practice with clinical features of urinary tract infection. Please rank the following fictional antibiotic treatments from most to least preferred in this scenario by dragging and dropping boxes or using the drop down menus on the left.

		AWaRe class*	C difficile risk	Toxicity risk	UTI specificity	Oral option	IV option	Cost
	Declozone	Watch	Low	High	No	No	Yes	High
	Choriotroban	Access	Low	High	No	No	Yes	Low
	Acetemran	Watch	Low	Low	Yes	Yes	No	Low
	Olanzasys	Watch	High	Low	No	No	Yes	Low
	Pansolid	Access	Low	Low	No	Yes	No	Low
	Protestryl	Watch	High	Low	No	Yes	Yes	Low
	Endoxolol	Access	Low	Low	Yes	Yes	No	Low
	Adenomadin	Access	High	Low	No	Yes	Yes	Low
	Abelfenide	Reserve	Low	Low	No	Yes	Yes	High
	Dexaset	Access	Low	Low	No	Yes	Yes	Low
	Adrevenac	Watch	High	Low	No	No	Yes	High
	Cormide	Watch	Low	Low	No	No	Yes	High
	Amrodine	Reserve	High	Low	No	No	Yes	High

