AWaRe class, nephrotoxicity and risk of *Clostridioides difficile* diarrhoea. Stakeholder consultation by questionnaire will help to inform these sections of the algorithm. Participants in this element of the study will be:

- General Practitioners
- Antimicrobial Pharmacists
- Medical Microbiologists
- Infectious Diseases Physicians
- Acute Medicine Physicians
- Accident and Emergency Physicians
- Bacteriology senior biomedical scientist

Invitations to participate will be disseminated by all-user trust email, with compensation offered for participant time (within sponsor allowances). Participation will be outside time dedicated for clinical care. Formal informed consent of participants will be sought in writing via email, with opportunities for participants to ask questions provided via email and Microsoft Teams. The participant consent form is enclosed in Appendix 1. Once consent has been obtained, participants will be provided with a questionnaire (enclosed in Appendix 2) asking them to rank pseudonymised antimicrobials by order of appropriateness based on several factors. These findings will be analysed by linear regression to output regression coefficients, which will be considered for incorporation into the selection algorithm.

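### The 13 questionnaire profiles never vary toxicity among oral products or cost outside Watch, so some weights are needlessly imprecise; changing two cells cuts the toxicity, cost and Reserve-vs-Access variances by 42% to 51%

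*Protocol*

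**What the plan says.** Section 3.3.1 lists measures that may be needed to steer the choice of antimicrobials for testing. They include weighting for AWaRe class, nephrotoxicity and *C. difficile* risk. It then says: "Stakeholder consultation by questionnaire will help to inform these sections of the algorithm". On analysis it says: "These findings will be analysed by linear regression to output regression coefficients, which will be considered for incorporation into the selection algorithm".

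Appendix 2 prints the instrument. The scenario is a patient in general practice with features of UTI, and the task is: "Please rank the following fictional antibiotic treatments from most to least preferred in this scenario". There are 13 invented products described on seven attributes: AWaRe class at three levels, and *C. difficile* risk, toxicity risk, UTI specificity, oral option, IV option and cost at two levels each.

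The protocol gives no rationale for the profile set, no number of respondents and no precision target for the coefficients.

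**The concern.** The questionnaire exists to separate the influence of these attributes on preference. Two pairs of attributes are tied together in the table. All Access products are cheap and both Reserve products are expensive, so with AWaRe entered as classes, cost is contrasted only within Watch. The two high-toxicity products, Declozone and Choriotroban, are both IV-only, so no respondent ever judges a toxic product that can be taken by mouth.

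The coefficients may be used to choose among real agents, and section 3.3.1 wants a mixture of oral and IV agents on each panel. A toxicity weight carried to an oral agent would then have no direct observation behind it. The toxicity, cost and Reserve coefficients would also be noisier than 13 profiles need make them. The products are invented, so the table can be changed freely before it is sent.

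**Working it through.** The plan states no precision for these coefficients, so there is no figure to reproduce. The check uses only the 13 rows of Appendix 2.

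**Counts from the table**

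| | High | Low |
|---|---|---|
| Cost, Access | 0 | 5 |
| Cost, Watch | 3 | 3 |
| Cost, Reserve | 2 | 0 |
| Toxicity, IV-only | 2 | 4 |
| Toxicity, oral and IV | 0 | 4 |
| Toxicity, oral-only | 0 | 3 |

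**Model.** Main effects by ordinary least squares: an intercept, two AWaRe indicators (reference Access) and six two-level attributes, giving a 13 × 9 matrix X. All respondents rank the same profiles. With equal, independent errors of variance σ² and n respondents, Var(b) = (σ²/n) × diag[(X'X)⁻¹]. Neither σ² nor n is stated, but both cancel in ratios.

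**Current design.** X has rank 9 of 9, so every main effect is estimable. The Reserve and cost estimates correlate at −0.69, and toxicity and oral option at +0.54. Variance inflation factors are 2.18 for toxicity, 3.00 for Reserve and 3.54 for cost. Adding a toxicity-by-oral column leaves the rank at 9 of 10 columns, so that interaction cannot be estimated. The same holds for cost-by-Watch.

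**Two cells changed.** Protestryl toxicity Low to High; Adenomadin cost Low to High. Variances are in units of σ²/n:

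| Term | Now | Changed | Difference |
|---|---|---|---|
| Toxicity | 1.287 | 0.631 | −51% |
| Cost | 1.149 | 0.600 | −48% |
| Reserve vs Access | 1.770 | 1.022 | −42% |
| Oral option | 0.851 | 0.506 | −41% |
| *C. difficile* risk | 0.736 | 0.454 | −38% |
| Watch vs Access | 0.713 | 0.539 | −24% |
| Reserve vs Watch | 1.011 | 0.882 | −13% |
| IV option | 1.563 | 1.655 | +6% |

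The sum over the eight coefficients (Reserve vs Watch is a derived contrast, not one of them) falls from 9.75 to 7.04, or 28%. The two correlations fall to −0.40 and +0.07. If AWaRe is scored 0/1/2 instead, its variance falls from 0.429 to 0.239 (−44%).

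Under the model, the ratios equal a gain in respondents: 1.287/0.631 = 2.0 for toxicity, 1.149/0.600 = 1.9 for cost and 1.770/1.022 = 1.7 for Reserve vs Access.

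**What the change does not buy.** With toxicity-by-oral added to the changed design, the rank is 10 of 10. But the interaction has variance 6.23, and the toxicity effect among oral products has variance 3.16, because it rests on Protestryl alone. Both Reserve products are still expensive, so cost is still not contrasted within Reserve.

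**The choice of cells matters.** Putting both changes on Dexaset leaves the toxicity variance where it was (1.287 to 1.299).

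**The case against.** The strongest reply is that the design works as it stands. It has full rank, Watch is balanced 3/3 on cost, and the inflation factors are moderate. A reader might infer from the table that dislike of cost will be read as dislike of Reserve. The documents do not support that. Under the main-effects model, cost is estimated within Watch and removed from the Reserve contrast. The result is imprecision, and bias arises only if the effects are not additive. That reply stands.

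A reader might also infer that the two-cell change halves the variance of every AWaRe weight, or that it settles toxicity for oral products. Neither follows: two of the three AWaRe contrasts improve by only 24% and 13%, and the oral toxicity effect would hang on one profile. The 51% gain for toxicity holds only under additivity.

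Material harm is not shown. As an illustration only, take the full standard deviation of ranks 1 to 13, √((13² − 1)/12) = 3.74, as a rough ceiling for σ, and assume 20 to 200 respondents. The standard error for Reserve vs Access, 3.74 × √(1.770/n), is then at most 1.11 to 0.35 rank places. After the change it is 0.85 to 0.27. More respondents would also shrink it. Use of the coefficients is conditional, and cost is not among the stewardship factors that section 3.3.1 names as examples.

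More respondents cannot, however, supply a contrast that the table lacks. Realism may explain the pattern, but the protocol does not say so.

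**Conclusion.** The point holds as a cheap improvement to the instrument. Toxicity is never contrasted among products with an oral option, and cost is contrasted only within Watch when AWaRe enters as classes. Both statements are counts and need no model. The planned regression remains estimable; its toxicity, cost and Reserve-vs-Access coefficients have about 1.7 to 2.0 times the variance that a two-cell change would give.

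The percentages rest on a main-effects model with equal, independent errors, which ranks only approximate. The fixed sum of each respondent's ranks does not by itself alter the ratios, because a common correlation rescales all slope variances alike. Real differences between respondents in how they weigh attributes would add variance that no profile change removes, so the equivalent gain in respondents could be smaller. Whether any panel choice would change cannot be judged from the protocol.

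**What to change.** **If the questionnaire has not been sent:** in Appendix 2, set Protestryl's toxicity risk to High and Adenomadin's cost to High. If another pair is preferred, recompute the variances first, since some pairs give no gain for toxicity. The cost is two table cells and a small amendment, a 6% rise in the IV-option variance, and profiles that may look less like real products. No clinical rule is touched.

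**If answers are already in:** keep the analysis. State in the report that the toxicity weight for oral agents and the cost weight outside Watch rest on additivity, and show how far the selected panels change when those weights are varied. Setting the oral toxicity weight to zero is not a safe default, because the 13 profiles support it no better than additivity. This costs a sensitivity analysis and a sentence of explanation.

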### 9.3 Appendix 3 - Data Management plan

**What stage are you at in this project?**

- Post-award

**Which faculty do you belong to?**

- Health and Life Sciences

**Do you have, or will you be applying for Ethics approval for your project?**

- Yes

**Will be you collecting and storing personal or sensitive data as defined under the terms of GDPR? (this includes email addresses, phone numbers, etc)**

- No

**Will you require space on the Active DataStore?**

- No

**If you are not using the ADS, where will you store your data?**

- Cloud Store

**Will you be depositing your data in an open repository at the conclusion of your project?**

- No

**Your research data**

**What types of data will be collected or created?**

The project will analyse linked, pseudonymised demographic, past medical, hospital admission, general practice consultation, prescribing, microbiology and other laboratory pathology specimen data.

**What formats will you use?**

Comma Separated Values files

**How much data do you estimate you will be collecting and storing?**

~ 80-100 columns

~ 250,000-1,000,000 rows

Estimated file size would be between 3GB and 4GB

**Documentation**

**Are there any standards for organising, labelling or describing research data in your field of research. If so, detail below.**

Systematised Nomenclature of Medicine Clinical Terms (SNOMED-CT), an international clinical terminology metadata library.

**Ethics and Intellectual Property**

**Who owns the data you will be using, creating or collecting?**

Data will be owned by Cheshire and Merseyside Integrated Care Board who manage the CIPHA service and access to this dataset. Prior data protection impact assessments and data sharing agreements have been completed by University Hospitals NHS Foundation Trust and all participating general practices.

**Are there any legal, ethical or commercial considerations? If so, how do you propose to deal with them?**

The possible risk of reidentification is negligible owing to the pseudonymisation process – project team members must take personal responsibility for data security, working in a way that prevents legal and procedural breaches. Project team members will ensure that statistical disclosure controls are in place on output data to ensure that reidentification is not possible from results.

**Storage and Organisation**

**Where will the data be stored during your project? If you are not using UoL managed drives, explain why.**

The NHS Cheshire and Merseyside Integrated Care board / Combined Intelligence for Public Health Action (CIPHA) secure data environment.

**Are there any security issues relating to the storage of the data?**

The data will be de-identified and will not leave the NHS-managed and provided secure environment. Only named and approved ADAPT-AST project members will be given access to the data.

**Who else will have access to this data during the project?**

NHS ICB-employed data engineers within the NHS ICB/CIPHA secure data environment.

**Data Sharing**

**Will you be able to share any of your data in an open access repository?**

Statistically derived aggregate data may be shared in publication.

**If not 'open', who could have access to your data and how would this be facilitated?**

Any shareable data could be shared using the Liverpool Data Catalogue, with any share data directed to by a data statement in any publications.

**What formats do you anticipate the data will be shared in?**

Not applicable

**Long Term Archiving**

**Will there be any data that you cannot share but will need to be retained in the long term?**

Pseudonymised study data and code key will be archived within a password-encrypted secure data environment within the ICB/CIPHA SDE for 10 years.

**Where will the data be archived at the end of the project and how long will it be retained?**

The research team will request that data be archived for 10 years within the NHS CIPHA Secure Data Environment.

**What formats do you anticipate the data will be archived in?**

Not applicable - formatting will be set by CIPHA
